1.2.7 Safety analyses

1.2.7.1 Physical examination

As the clinically significant abnormality in physical examination is not recorded in the database, only the number and percentage of participants with at least one post-baseline abnormality in physical examination will be summarized and listed by treatment group.

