1.4 SCHEDULE OF ACTIVITIES - HEALTHY PARTICIPANTS

| Phase | Screening | Observational phase | EoS |
|--|----------------------|---------------------|-----------|
| Day | D -21 to D -1 | D1 | D8 |
| Visit | 1 | 2 | 3 |
| Informed consent | X | | |
| Visit at clinical site | X | X | X |
| Inclusion/exclusion criteria | X | X | |
| Demographics | X | | |
| Medical/surgical history, demographics | X | | |
| Prior/concomitant medications | <----- X -----> | | |
| Skin biopsy | | X | |
| Blood sample | | X | |
| Safety | | | |
| Physical examination | X | | |
| Height | X | | |
| Body weight | X | | |
| Serology tests | X | | |
| IgE | X | | |
| Adverse event collection | <----- X -----> | | |
| Photography | | X | |

Abbreviations: D: day; EoS: end of study; V: visit.

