5.1.1 Atopic dermatitis patients

Age

I 01. Male or female of ≥ 18 years of age inclusive, at the time of signing the informed consent form (ICF).

Type of participant and disease characteristics

I 02. Diagnosed with moderate-to-severe chronic AD for at least 1 year before screening.

I 03. Eligible to be treated with dupilumab according to product monograph.

I 04. Pruritus lasting 6 or more weeks before baseline (Day 1).

I 05. Eczema Area and Severity Index (EASI) score ≥ 12 at baseline.

I 06. Pruritus numerical rating scale (NRS) ≥ 4 at baseline.

I 07. Investigator global assessment (IGA) score of ≥ 3 at screening (on the 0 to 4 scale) at baseline.

I 08. Atopic dermatitis active lesions on the upper limbs or lower limbs suitable for a skin biopsy without oozing, bleeding, or infection on upper limbs or trunk.

I 09. Patients with acute AD lesions as determined by Investigator's judgment.

I 10. Participants able to accept skin biopsy procedure.

- I 11. Participants willing to refrain from applying any emollients or topical medications on the target assessment areas (including lesional and non-lesional) throughout the study unless necessary to treat intolerable symptoms.
- I 12. Participants willing and able to comply with all site visit and study-related procedures.
- I 13. Participants able to understand and complete all patient related outcome assessments and questionnaires.

Concomitant medication

- I 14. Stable treatment with non-prohibited medication ([Section 6.5.2](#)) or therapy during the study.

Informed consent

- I 15. Capable of giving signed informed consent which includes compliance with the requirements and restrictions listed in the ICF and in this protocol. In countries where legal age of majority is above 18 years, a specific ICF must also be signed by the participant's legally authorized representative.

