8.4.1 Physical examinations

- A complete physical examination will include, at a minimum, assessments of the skin, cardiovascular, respiratory, and neurological systems. Height and weight will also be measured and recorded.
- Signs and symptoms of hypersensitivity reaction (if any) will be documented.
- A skin focused physical examination will be performed prior to each skin biopsy assessments at time points according to SoA ([Section 1.3](#) and [Section 1.4](#)).
- Investigators should pay special attention to clinical signs related to previous serious illnesses.
- Any new finding or worsening of previous finding should be reported as a new AE.

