9.4.8.2 Vital signs

For AD participants, heart rate, systolic and diastolic blood pressures (SBP and DBP), and body temperature will be analyzed as raw parameter value and change from baseline.

Body weight will be analyzed as raw parameter value. BMI will be analyzed as raw parameter value.

Baseline definition

The values to be used as baselines will be the Day 1 (Visit 2) predose assessment. If any of the scheduled baseline tests are repeated for any participant, the last rechecked values will be considered as baselines, provided, for patients, they were done before the IMP administration, and in the same condition.

Abnormalities analyses

For all vital sign parameters, analysis will be performed using all post-baseline assessments done during the TEAE period/safety period, including all unplanned and rechecked values. Potentially clinically significant abnormality (PCSA) values are defined as abnormal values considered medically important by the Sponsor according to predefined criteria/thresholds based on literature review and defined by the Sponsor.

Potentially clinically significant abnormality (PCSA) Listings

A listing of individual data from participants with post-baseline PCSAs will be provided; values will be flagged when reaching the PCSA criteria.

9.4.8.3 *Physical examination*

Participants with at least 1 clinically significant abnormality in physical examination will be summarized and listed by treatment group.

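### The SAP's physical examination count ignores baseline, so it mixes persisting eczema with new findings, and on the schedules it has no healthy denominator

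*SAP*

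**What the plan says.** Protocol 9.4.8.3 planned a table with a severity filter: "Participants with at least 1 clinically significant abnormality in physical examination will be summarized and listed by treatment group". SAP 1.2.7.1 removes the filter. Its reason is "As the clinically significant abnormality in physical examination is not recorded in the database", and the replacement is that "only the number and percentage of participants with at least one post-baseline abnormality in physical examination will be summarized and listed by treatment group". It adds no condition on baseline status, new onset or worsening, and no split by body system.

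The surrounding text that decides what this rule will count:

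- **Content of the examination.** Protocol 8.4.1 requires "assessments of the skin, cardiovascular, respiratory, and neurological systems". It adds that "A skin focused physical examination will be performed prior to each skin biopsy assessments", and refers to both schedules for the timing.
- **Skin at entry.** Protocol 5.1.1 requires "Eczema Area and Severity Index (EASI) score ≥ 12 at baseline", an IGA of at least 3, and acute AD lesions.
- **Timing.** The AD schedule (Protocol 1.3) marks physical examination at screening, Day 1 and Week 21. The healthy schedule (Protocol 1.4) marks it at screening only.
- **Baseline.** Under Protocol 9.4.3.3 the safety baseline is the last pre-dose value for AD participants and the last screening value for healthy participants.
- **Treatment-emergent period.** SAP 1.2.1 ends it at the end-of-treatment visit, which is Week 17.
- **Usable data.** SAP 1.3 restricts post-baseline descriptive statistics to observations the protocol planned.

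**The concern.** In a safety table a post-baseline abnormality is informative when it was absent, or milder, before treatment. Here the disease under study is itself an abnormality of one of the systems examined, and eligibility guarantees that it is present on Day 1. A participant whose eczema has improved but not cleared by Week 21 falls into the same cell as one with a new cardiovascular or neurological finding.

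The plan follows the baseline principle elsewhere. Every vital-sign criterion in SAP 3.1 needs both a threshold and a change from baseline. Protocol 8.4.1 directs attention to new or worsened findings, and Protocol Appendix 3 keeps expected signs of the studied disease out of the adverse events unless they are more severe than expected. SAP 1.2.7.1 departs from all three.

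What is at stake is the meaning of one table. A percentage presented by group would be read as a safety result, although in the AD group it may mostly reflect how much eczema remains, and in the healthy group nobody is scheduled to be examined after baseline.

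**Working it through.** The documents give no figure for physical examination abnormalities, so there is nothing to reproduce. The check has two parts.

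**1. When examinations take place**

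| Group | Examinations marked in the schedule | Safety baseline | Marked after baseline |
|---|---|---|---|
| AD (34) | Screening, Day 1, Day 141 (Week 21) | Last pre-dose, Day 1 | 1 (Week 21) |
| Healthy (up to 10) | Screening | Screening | 0 |

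- The last scheduled dose is on Day 99, so the Week 21 examination falls 141 − 99 = 42 days later.
- The treatment-emergent period ends on Day 113, so the examination falls 141 − 113 = 28 days after it closes.
- The healthy percentage has a numerator and a denominator of zero. It is undefined, not 0 out of 10.

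Protocol 8.4.1 gives a different picture. A skin-focused examination before each biopsy would fall at Week 17 for all AD participants, at Weeks 3 and 21 for those with optional biopsies, and on Day 1 for healthy participants. Neither schedule has a row for it, so it is unclear whether SAP 1.3 treats it as planned. If it does:

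- AD participants gain further occasions to be counted, and the number differs between participants because some biopsies are optional.
- Healthy participants gain an examination after their screening baseline but still before the biopsy, so it cannot show a finding caused by the biopsy.

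**2. What the count contains (illustration)**

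Let p be the proportion of examined AD participants whose AD skin signs are still recorded as abnormal, and q the proportion with a new or worsened finding. Both are assumptions, and they are treated as independent.

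- Proportion counted by the SAP rule = 1 − (1 − p)(1 − q)
- Share of those counted who have something new = q / [1 − (1 − p)(1 − q)]

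The number examined is also an assumption. Applying the protocol's 20% drop-out allowance gives 34 × 0.8 = 27.2, taken as 27. With q = 5%:

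| p | Proportion counted | Participants counted of 27 | With a new finding | Share new |
|---|---|---|---|---|
| 20% | 1 − 0.80 × 0.95 = 24% | 6.5 | 1.4 | 21% |
| 50% | 1 − 0.50 × 0.95 = 52% | 14.2 | 1.4 | 10% |
| 80% | 1 − 0.20 × 0.95 = 81% | 21.9 | 1.4 | 6% |

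Over p = 20% to 80% and q = 2% to 10%:

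- The proportion counted runs from 1 − 0.80 × 0.98 = 22% to 1 − 0.20 × 0.90 = 82%.
- The share new runs from 0.02 / 0.804 = 2% to 0.10 / 0.28 = 36%.
- At p = 0 the share new is 100%, so the distortion disappears if skin clears fully or sites do not record known AD as abnormal.

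**The case against.** The strongest reply is that the safety information is held elsewhere. Protocol 8.4.1 requires new or worsened findings to be reported as adverse events. Protocol 9.4.8.1 lists all adverse events, tabulates the treatment-emergent ones by system organ class and preferred term, and summarises separately those outside that period or in healthy participants. Protocol 9.4.8 bases the safety evaluation on vital signs and adverse events and does not name physical examination. With at most 44 participants, the individual listings can be read person by person. The sponsor's reporting templates cited in SAP 1.1 are not available to us and may shape the layout. This stands, and it limits the harm to a table that cannot be interpreted.

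Three stronger readings are tempting and are not supported:

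- **That the table shows only eczema.** The count also includes cardiovascular, respiratory and neurological findings, and new skin findings. It mixes them with eczema and does not replace them.
- **That healthy participants supply a zero against which dupilumab shows a spurious excess.** On the schedules their denominator is empty. They are a reference for the biopsy endpoints, and no document plans a between-group comparison of examinations.
- **That most AD participants will certainly be counted.** No document gives a clearance rate at Week 21 or says how sites record known AD.

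The reply does not rescue the rule itself. A row that needs the adverse event tables to be understood adds nothing to them, and the listing does not make the percentage interpretable.

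**Conclusion.** The point holds as a defect in the stated counting rule, worth correcting but with limited consequences. The absence of a baseline condition, the inclusion of skin and the requirement for active eczema at entry are all explicit. Together they mean the count cannot separate persisting or improved eczema from a new finding. On the schedules the AD result is also a post-treatment result, and the healthy result has no denominator.

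The direction is firm unless p is close to zero, but the size is not known. The ranges in the working rest on assumed values of p and q, on their independence and on an assumed number examined. They illustrate the problem and do not predict the table.

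Separately, Protocol 8.4.1 and the two schedules disagree on whether the skin is examined at the biopsy visits, and they must be reconciled.

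**What to change.** In SAP 1.2.7.1:

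- Count participants with findings that are new or worsened relative to the last pre-dose examination, by body system where that was recorded.
- Give skin its own row for AD participants, with baseline skin status alongside. A normal-to-abnormal shift alone would not do, because skin is abnormal at baseline in all of them and new skin findings would drop out.
- If worsening or body system was not recorded, say so in a footnote and refer the reader to the adverse event tables.
- List unchanged baseline abnormalities separately.
- State the number examined, and label the Week 21 examination as post-treatment.
- Show healthy participants as having no post-baseline examination, unless one is planned.

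Reconcile Protocol 8.4.1 with the schedules in 1.3 and 1.4, and state in the SAP whether the pre-biopsy skin examinations count as planned observations. If collection has finished, which the SAP's account of the eDiary data suggests may be close, state instead where those examinations were recorded.

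The analysis change costs SAP wording and table programming, with no new visit. How far the split by body system and the worsening condition can be applied depends on what the database holds, which the documents do not show. Correcting the schedules would need a protocol clarification or amendment.

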1.3 DATA HANDLING CONVENTIONS

This section describes the rules and conventions used in the presentation and analysis of data.

In the statistical appendices and in-text tables, the following study group label will be used:

- Healthy Participant.
- Dupilumab (*identified as “patient group” in the protocol*).

All individual data for all included participants will be presented in data listings, sorted by study group and participant number.

In listings, no date of assessments/events/medications will be presented but only the relative day. It will be calculated as follows:

- For AD participants: relative day = date of assessments/events/medications – date of first IMP administration +1.
- For healthy participants: relative day = date of assessments/events/medications – date of D1 visit +1.

For parameters with evaluations before administration and in cases of rechecked value(s) for one participant, only the last observation will be used as baseline in descriptive statistics and derivations of other parameter values. After baseline, only observations planned in the protocol will be used in descriptive statistics.

If not otherwise stated in the statistical section of the protocol:

- Missing data other than protocol-planned baseline values will not be replaced.
- Descriptive statistics for quantitative parameters will be provided using number of observations (N), mean, standard deviation (SD), SEM, median, minimum and maximum. The 95% confidence interval will be added for efficacy analyses.
- Descriptive statistics for qualitative parameters will be provided using frequencies (N) and percent (%).

Handling missing data for adverse events

In case of missing or inconsistent information, an AE will be counted as a treatment-emergent AE (TEAE), unless it can clearly be ruled out that it is not a treatment-emergent adverse event (eg, by partial dates or other information).

If the start date (or time) of an AE is incomplete or missing, it will be counted as TEAE except if an incomplete date (or time) or comment indicates that it is a pre- or post-treatment event.

If the relationship to study intervention is missing for an AE, this AE will be assessed as unrelated if it started before administration of study medication; in all other cases it will be assumed to be related.

If the severity is missing for one of the treatment-emergent occurrences of an AE, the severity will be imputed with the maximal severity of the other occurrences. If the severity is missing for all the occurrences, the severity will be left as missing.

2 SOFTWARE DOCUMENTATION

The analysis of clinical data will be performed under the responsibility of Sanofi Biostatistics Department, using SAS® (SAS Institute, NC USA).

3 APPENDICES

3.1 POTENTIALLY CLINICALLY SIGNIFICANT ABNORMALITIES CRITERIA

CRITERIA for POTENTIALLY CLINICALLY SIGNIFICANT ABNORMALITIES for Phase 2/3 studies (oncology excepted)		
Parameter	PCSA	Comments
Vital signs		
HR	≤50 bpm and decrease from baseline ≥20 bpm ≥120 bpm and increase from baseline ≥20 bpm	To be applied for all positions (including missing) except STANDING.
SBP	≤95 mmHg and decrease from baseline ≥20 mmHg ≥160 mmHg and increase from baseline ≥20 mmHg	To be applied for all positions (including missing) except STANDING.
DBP	≤45 mmHg and decrease from baseline ≥10 mmHg ≥110 mmHg and increase from baseline ≥10 mmHg	To be applied for all positions (including missing) except STANDING.
